iSupport-PD: a digital intervention for care partners of people with Parkinson's and cognitive impairment

(iSupport-PD)

Statistical analysis and Health Economics Analysis Plan

Version 1

Date: 10/11/2025

Contents

Se	ection 1: Administrative Information	3
2:	Design	. 4
3:	Trial Objectives	. 4
4:	Randomisation	. 4
5:	Outcomes	. 4
	5.1 Primary outcome	. 4
	5.2 Secondary Outcomes	5
	5.3 Follow-up	6
6:	Data	7
	6.1Data monitoring	7
	6.2 Sources of data	8
	6.3 Management of datasets	8
7:	Analysis	8
	7.1 Screening, eligibility, recruitment and follow-up data	8
	7.2 baseline data	8
	7.3 Statistical Analysis	. 8
	7.5 adverse events	9
	7.6 Protocol non-compliance/deviation	9
	8 Health Economics Analysis plan	9
	8.1 Aims	9
	8.2 Analysis	9
	8.2.1 Costs	9
	8.2.2 Health-related quality of life	10
	8.3 Cost-effectiveness analysis	10
	8.4 Missing data	11
	8.5 Sensitivity analysis	12
	References	12

Section 1: Administrative Information

Title	
Trial registration number; registry	ISRCTN16483203 Prospectively registered on 07/06/2024
Source of funding	National Institute for Health Research – School for Social Care Research
Purpose of SAP/HEAP	To describe the planned statistical and health economic analysis for the ISupportPD feasibility RCT

Approvals

The following people have reviewed the Health Economics Analysis Plan and are in agreement with the contents.

Role	Name	Signature	Date
Economist/Statistic ian	[name]	ma	10/11/2025
Chief Investigator	[name]	[name]	10/11/2025

This statistical and health economics analysis plan deals with the statistical and economic analysis of the iSupportPD feasibility study. This analysis plan was prepared following recruitment but prior to completion of data collection and database lock.

2: Design

The iSupport-PD study is a parallel, two-arm, feasibility RCT with a 1:1 allocation ratio and includes an embedded pilot health economic analysis and mixed-methods process evaluation. Participants will be recruited in the UK, and the study runs for 20 months (1st July 2024 to 28th February 2026). The trial is registered ISRCTN16483203.

The two arms of this feasibility trial are:

- Intervention (access to iSupportPD)
- Control (usual care/no access to iSupportPD)

Full details of the background and design of the trial are presented in the protocol (version 9.0, dated 13th January 2025).

3: Trial Objectives

The primary research aim of this study is to determine the feasibility of conducting a powered randomised controlled trial (RCT) to investigate the clinical and cost effectiveness of the SPARC intervention. Specifically, to determine the following:

- 1. Recruitment, retention, and attrition rates of participants in the trial
- 2. Understanding the comparator (what does usual support look like?)
- 3. Potential effect sizes and variability to inform sample size calculations in an effectiveness trial
- 4. Feasibility of collecting outcome data
- 5. Engagement with intervention

Secondary aims include:

- Conducting a prospective economic evaluation to develop and refine methods for a subsequent definitive trial
- 2. Conducting a mixed-methods process evaluation to explore intervention and trial acceptability

4: Randomisation

Randomisation will be performed on a 1:1 basis by computer using dynamic allocation, in particular minimisation, to ensure groups are balanced for carer age, relationship to person with PD, gender. Use of dynamic allocation will also protect against subversion of randomisation. Allocation will be hidden using the sealed envelope method whereby the information needed for randomisation, collected at baseline, will be placed in an opaque sealed envelope by a researcher and given to a separate researcher to conduct the randomisation independently.

5: Outcomes

5.1 Primary outcome

The primary outcome for this study is to determine the feasibility of conducting a larger powered RCT. This will include outcomes such as successful recruitment to target, data collection completeness, intervention engagement, study attrition rate.

Data on numbers of participants identified, recruited, commences and finished intervention will be collected during the trial and reasons for declining participation or withdrawal will be recorded where possible. Feasibility of outcome measures and data collection will be

measured as number of participants completing pre and post follow-up outcome measures.

5.2 Secondary Outcomes

Secondary outcomes include validated outcome measures, NHS and social care resource use and other cost data (health economics), participant demographics such as age, relationship to person with Parkinson's, gender.

Validated outcomes measures can be grouped into carer burden, mental health, process, and quality of life measures. Caregiver burden will be measured using the short form 12-item Zarit Burden interview (ZBI-12). Item responses range from 0 (never) to 4 (almost always), and higher scores indicate greater distress.

Mental health measures consisted of scales to capture depression and anxiety. Depression will be measured using the Center for Epidemiologic Studies Short Depression Scale (CES-D-10). The CES-D-10 consists of 10 questions each with 4 responses from 'rarely or none of the time (less than 1 day)' to 'all of the time (5-7days)'. Anxiety will be measured using the generalised anxiety disorder scale (GAD-7 scale) which consist of asking caregivers to respond to seven questions around different areas of anxiety they have felt over the previous two weeks, each with four possible responses from 'Not at all" to "Nearly every day".

Process measurements include resilience, quality of relationship, self-efficacy, and carer burden. Resilience will be measured using the Resilience Scale (RS-14) which consist of 14 questions grouped into areas of self-reliance, purpose, equanimity, perseverance, and authenticity. Each question has a response between 1 (strongly disagree) to 7 (strongly agree). Quality of relationship will be measured using the Dyadic Relationship scale. This consist of 11 questions measuring the impact of the provision and receipt of family care. There are four levels of response to each question. Strongly Agree (0) to Strongly Disagree (3). Self-efficacy will be measured using the General Self-Efficacy scale(1) which consists of 10 questions with 4 responses to each question from 'not at all true' to 'Exactly True'. The positive aspects of caregiving scale (PACS) ((2)) consists of nine items related to positive aspects of caregiving each with a five response scored Likert scale from 'disagree a lot (1)' to 'agree a lot (5)'. An overall PAC score can be calculated (ranging from 9 to 45) with a higher score reflecting a more positive perception of the caregiving experience.

Quality of life measures include the Parkinsons Disease Questionnaire for carers (PDQ-C) will be used to measure quality of life of carers. The PDQ-C includes 29 questions covering different aspects of caring, with five response scale from 'never' to 'Always'. This is a validated measure for measuring quality of life for carers of persons with Parkinsonism and other related disorders. Health related quality of life will be measured using the EuroQol-5 Dimension EQ5D-5L(3). The EQ-5D-5L comprises five domains each assessing a specific dimension of health- related quality of life (mobility, self- care, usual activities, pain and anxiety and depression) with five response levels ('no problems', 'slight problems' 'moderate problems', 'severe problems' and 'extreme problems'). In addition, social care related quality of life will be measured using the ASCOT-Carer SCT4. This is a version of the Adult Social Care Outcomes Toolkit (ASCOT) designed for carers and consists of seven questions focused on areas of quality of life important to carers and sensitive to outcomes of social care services (occupation, control over daily life, self-care, personal safety, social participation and involvement, space and time to be yourself, feeling encouraged and supported). Each question consists of for response options (ideal, no needs, some needs, high-level needs).

5.3 Follow-up

Online questionnaires will be used as the primary mode of data collection. Participants will be sent a personalised link to self-complete questionnaires online using Qualtrics. Data will be collected at baseline (T0),), 3 months after baseline (T1), 6 months after baseline (T2), and 12 months after baseline (T3). Baseline measure will be collected prior to randomisation and will include demographic data such as age, gender, ethnicity, marital status, sexual orientation, socioeconomic status, education level, carer relationship, usual carer support, length of caring. Where data collection surveys are not completed a reminder will be sent via email to prompt participants to complete. After this, researchers will contact participants and collect data through interview via telephone or internet-based service. Although effort will be made to obtain follow-up data as close as possible to the relevant timepoints, it is anticipated that there may be some variation. T1, T2, and T3 follow-up will be acceptable up to 2 weeks early and 4 weeks late. Data will be stored on a secure password protected, purposely designed electronic database. Each participant will be randomly assigned a trial identify code at the point of their randomisation for use on CRF forms, electronic database, and other trial documentation. CRF data and electronic forms will be treated as confidential documents and held securely in accordance with regulations. The researcher will make an independent, separate, and confidential, record of participant name, age, date of birth, and trial number to permit identification of all trial participants as needed.

[figure not shown]

Figure 1: Planned flow of participants through trial

6: Data

6.1Data monitoring

Trial processed and data will be monitored throughout the trial with updated provided monthly at the trial management group meetings. Data collected during the course of the trial will be checked during the trial to offer quality assurance. As this is a feasibility trial, quality assurance will also allow the team to assess issues such as incomplete data collection forms, which may suggest misunderstanding, unwillingness to complete certain questions, or misunderstanding of data collection forms. This will contribute to the findings of the feasibility study and allow flexibility and changes to trial processes during the trial (with changes to the protocol noted and ethical approval for adjustments sought where necessary.

All study documentation will be retained in a secure location during the conduct of the study. Personal identifiable details such as names and contact details will be retained on a password protected database until required and then destroyed. All electronic data will be stored on secure network systems, to which only the relevant study personnel will have access. The dataset will be anonymised and stored securely

6.2 Sources of data

The Questionnaires (CRFs) consist of:

- -Screening form
- Baseline questionnaire
- -3 Month Follow-up questionnaire
- -6 Month Follow-up questionnaire
- -12Month Follow-up questionnaire

6.3 Management of datasets

The CRF forms are completed online. These online completed questionnaires are then downloaded and stored on a secure database. Each questionnaire will undergo a comprehensive data validation including: checks for completeness, appropriate data formatting, range checks. At the end of the trial follow-up, the dataset will be 'softlocked' and data quality will be checked across the whole dataset to check for consistency and any requested queries/amendments recorded. Once resolved, the database will be 'hard locked' where no further changes to the database will be allowed. Any further data changes/assumptions will be documented.

7: Analysis

All analyses will be conducted in STATA v15, under the principles of intention to treat (ITT) according to participant randomisation. The trial will report according to The Consolidated Standards of Reporting Trials (CONSORT) extension for reporting feasibility trials

7.1 Screening, eligibility, recruitment and follow-up data

For each time point, the number of questionnaires due and returned will be summarised, by arm and overall. This will detail how many were skipped, and for what reason.

Participants in this trial can withdraw from:

- Follow-up
- Fully (including death of the participant).

The number of withdrawals will be detailed by arm, by type. Additionally, the point at which the withdrawal occurred will be summarised.

7.2 baseline data

All participant baseline data will be summarised descriptively by trial arm both as randomised and as analysed in the primary analysis. No formal statistical comparisons will be undertaken. Continuous measures will be reported as means and standard deviations and categorical data will be reported as counts and percentages.

7.3 Statistical Analysis

Descriptive statistics will be used to determine the feasibility of conducting a larger powered randomised controlled trial. Analysis of outcome data will be conducted using an intention to treat approach, with patients analyses according to their treatment assignment. It will not be possible to collect outcome data for those who discontinue participation in the study. The data collected from outcome measures will be presented using summary statistics and differences

between intervention and control calculated at each follow-up points along with 95% confidence intervals. This data will help inform treatment effect estimates and sample size requirements for a larger powered RCT.

Progression criteria has been designed according to The Consolidated Standards of Reporting Trials (CONSORT) extension for reporting feasibility trials (4) and will enable interpretation of the findings of the feasibility study and inform whether a larger powered RCT is possible. Progression criteria will be assessed on a traffic light system of green/amber/red zones. Successful outcome of the feasibility trial would be to have all criteria assessed as green zones, suggesting no adjustments would be required for a future RCT. It is anticipated that progression to a future RCT would still be possible with a combination of amber and green zones but with potential adjustments implemented to mitigate risks highlighted in this feasibility study. Any red zone criteria would indicate that either the RCT trial design, or processes will need to be overhauled for any future RCT. All thresholds have been set based on levels that would enable completion of the trial objectives (Green without adaptation, Amber with adaptations to trial processes, Red/stop would not be possible to complete):

7.5 adverse events

It was not anticipated that any adverse events would occur in this trial. As such, no adverse events will be reported for this study

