8.4 Missing data

Missing data will be quantified per data item (%). Ignoring small amounts of missing data (e.g., <5% of the observations) is acceptable if the amount and pattern of missing data are similar across treatment groups and a reasonable case can be made that doing so is unlikely to bias treatment group comparisons. As total cost is calculated as a sum of numerous components, if one component is missing then the total cost will be missing. Such complete case analysis may introduce bias if those with complete data differ from those with partial data. The method to handle missing data will be grounded in a plausible assumption regarding the missing data mechanism. Rubin's framework will be utilised for classifying missing data in order to define assumptions and choose an appropriate analysis method for the base case. (11) If Missing At Random (MAR) is suggested, we will incorporate multiple imputation with chained equations (MICE) to deal with missing cost and utility data. Data are missing at random (MAR) if the probability that data are missing is independent of unobserved values, given the observed data (including previous outcome measurements). Therefore, any systematic differences between the observed and unobserved values can be explained by differences in observed variables. Although the linear mixed effect model proposed for the cost-effectiveness analysis can also be used to deal with missing data under a MAR assumption, it has several limitations compared to multiple imputation(12). Firstly, as the linear mixed model is pre-specified, it is inflexible and cannot adjust for potential observed variables which impact missing data. This contrasts with multiple imputation in which missing data is imputed using a separate model, which can be adjusted for observed variables driving missing data. Secondly, multiple imputation allows further flexibility and potential sensitivity analysis to be conducted around the imputed missing data variables. Furthermore, combination of multiple imputation around a linear mixed model analysis has been identified as more efficient in trial-based cost-effectiveness analysis compared to just using linear mixed effects models alone(13).

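### Section 7.3 names no baseline or covariate adjustment for the outcome scales, so intervals are wider than the design allows and the correlation useful for sizing the next trial is not reported

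*SAP*

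**What the plan says.** Section 7.3 holds the whole plan for the clinical scales: summary statistics, plus differences "between intervention and control calculated at each follow-up points along with 95% confidence intervals". It names no model, covariate, repeated-measures method or missing-data assumption. On loss to follow-up it adds: "It will not be possible to collect outcome data for those who discontinue participation in the study". Sections 7 and 7.3 both describe intention to treat as analysis by the arm to which a participant was randomised.

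Other sections show what is available and what the estimates are for:

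- Section 2 describes a "parallel, two-arm, feasibility RCT with a 1:1 allocation ratio".
- Section 3, objective 3, is "Potential effect sizes and variability to inform sample size calculations in an effectiveness trial". Section 7.3 repeats that purpose.
- Section 4 allocates by "minimisation, to ensure groups are balanced for carer age, relationship to person with PD, gender".
- Section 5.3: "Baseline measure will be collected prior to randomisation". Follow-up is at 3, 6 and 12 months (T1, T2, T3).
- Section 8.3 models costs and QALYs with allocation, time, their interaction, baseline utility and within-person correlation. Section 8.4 adds multiple imputation, for cost and utility data only.

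**The concern.** The baseline score is usually among the strongest predictors of a later score on the same scale. Leaving it out of the comparison discards precision that the trial has already paid for. Minimisation also makes the arms more alike on three factors than simple randomisation would. An interval that ignores those factors does not credit that balance and tends to be too wide.

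Objective 3 is where this costs most. If the next trial adjusts for baseline, its sample size depends on the residual SD, or equivalently on the outcome SD and the baseline/follow-up correlation. Section 7.3 provides for neither the residual SD nor the correlation.

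Finally, someone who answers at T1 and T2 but not at T3 contributes nothing to a visit-by-visit T3 difference, although the earlier answers carry information about the missing one. Section 8.3 already plans a longitudinal, baseline-adjusted model for costs and QALYs, so the approach is not foreign to the plan.

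**Working it through.** The SAP gives no sample size, SD, correlation, attrition rate or target effect, so there is no stated figure to reproduce. The inputs below are assumptions, shown over a range. Outcomes are in SD units, n is the number per arm, and ρ is the baseline/follow-up correlation.

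**1. Interval width.** In large samples the ratio of adjusted to unadjusted width is √(1 − ρ²):

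- ρ = 0.3: √0.91 = 0.954, about 5% narrower
- ρ = 0.5: √0.75 = 0.866, 13% narrower
- ρ = 0.7: √0.51 = 0.714, 29% narrower

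In small samples the unadjusted half-width is t(2n−2) × √(2/n). The baseline-adjusted half-width is t(2n−3) × √(2/n) × √(1−ρ²) × √(1 + 1/(2n−4)). At n = 30:

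| ρ | Unadjusted | Adjusted | Ratio |
|---|---|---|---|
| 0.3 | 0.517 | 0.498 | 0.963 |
| 0.5 | 0.517 | 0.452 | 0.874 |
| 0.7 | 0.517 | 0.373 | 0.721 |

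From n = 20 to n = 50 the ratio at each of these ρ changes by no more than 0.01, so the conclusion depends on ρ and hardly at all on n. These figures cover the baseline score only; the extra gain from the minimisation factors was not quantified.

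**2. Chance baseline imbalance.** The baseline difference between arms has SD √(2/n), which is √(2/30) = 0.258 at n = 30. It moves the unadjusted difference by ρ times the imbalance: an imbalance of 0.25 SD moves it by 0.125 SD at ρ = 0.5 and 0.175 SD at ρ = 0.7. This is not a second harm on top of step 1. At n = 30 and ρ = 0.5 the variance of the unadjusted difference is 2/30 = 0.0667. Baseline imbalance accounts for 0.25 × 0.0667 = 0.0167, leaving 0.0500, and √(0.0500/0.0667) = 0.866, the same ratio as in step 1.

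**3. Sizing the next trial.** Take, for illustration, an effect of 0.4 SD, 90% power and two-sided 5%, with n per arm = 2(1.960 + 1.282)² × (1 − ρ²)/0.4²:

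- without adjustment: 132
- ρ = 0.5: 99
- ρ = 0.7: 67

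Moving from the first figure to the others requires ρ or the residual SD.

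**4. Partial follow-up.** A simulation used 30 per arm, no true difference, equal correlations of 0.5 or 0.7 among baseline, an earlier visit and a later visit, and about 20% missing at the later visit.

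- Missing completely at random: all estimates are unbiased. The standard error is 0.29 for the unadjusted difference against 0.25 when baseline and the earlier visit are used (ρ = 0.5), and 0.29 against 0.20 (ρ = 0.7).
- Dropout in one arm dependent on the earlier score: the unadjusted available-case difference is off by 0.07 to 0.14 SD, baseline-only adjustment by 0.03 to 0.05 SD, and the estimate using baseline plus the earlier visit by about 0.

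The second case assumes that missingness depends only on observed scores. The SAP gives no evidence on whether that will hold.

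**The case against.** Much of the case on the other side stands, and it limits the point.

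- **A reader might infer that the SAP prescribes raw differences.** It does not use that word; the estimator is simply unnamed. Unadjusted is the natural reading, since no covariates are listed. If some other estimator is meant, the same text still has to be added.
- **A reader might infer that intention to treat is breached.** It is not. The SAP defines it as analysis by assigned arm, and a visit-by-visit contrast meets that definition. Nor can a model recover data never collected after discontinuation. It can only use earlier answers under a stated assumption.
- **A reader might infer that the estimates are biased by imbalance.** An unadjusted difference is unbiased over randomisations, and its interval already includes chance imbalance. That imbalance concerns the baseline scores. The minimised factors are balanced by design, and leaving them out mainly makes intervals conservative. Section 8.3 does not list them either.
- **A reader might set section 8.4's warning against 7.3:** "Such complete case analysis may introduce bias if those with complete data differ from those with partial data". In context it concerns total cost going missing when one component is missing, so it does not directly contradict 7.3.
- **An unadjusted SD is a legitimate planning input.** It would oversize the next trial only if that trial adjusts for baseline and nobody applies 1 − ρ². The SAP does not say how that trial will be analysed.
- **The stakes are limited.** Feasibility is the primary outcome, the scales are secondary, and 7.3 plans no hypothesis test. Sections 7.1 and 7.2 already report returns, withdrawals and baseline data by arm, so imbalance and selective loss will be visible.
- **A mixed model for each of about ten scales is demanding in a small trial.** Convergence and sparse relationship categories are real concerns, so the fix needs a fallback.

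**Conclusion.** The point holds as a moderate, inexpensive improvement to a descriptive secondary analysis. As naturally read, section 7.3 leaves unused the baseline scores and the minimisation factors, both of which the trial holds. The cost is intervals that adjustment would narrow by about 5%, 13% or 29% at assumed correlations of 0.3, 0.5 or 0.7; at the low end the gain is small. The more certain loss is that the plan does not report the baseline/follow-up correlation or residual SD, which objective 3 could use directly. Each visit is also an available-case contrast with no stated missing-data assumption. Whether that causes bias depends on the dropout pattern, and the documents give no figure for it. No error rate or confirmatory conclusion is affected.

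**What to change.** In section 7.3:

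- For each scale, estimate the arm difference and 95% CI at T1, T2 and T3 from a linear mixed model over the three visits, with arm, visit, arm × visit, the scale's baseline score, and carer age, relationship and gender.
- Include everyone with at least one follow-up, in the arm as randomised, and state that the analysis assumes data are missing at random.
- Name per-visit ANCOVA with the same covariates as the fallback if the mixed model does not converge, and state in advance how sparse relationship categories will be merged.
- Report the outcome SD, residual SD and baseline/follow-up correlation for each scale.
- Keep the unadjusted summaries and differences as a supplement.

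The cost is a paragraph of SAP text, a few degrees of freedom, possibly some merged categories, and a little more analysis work. No new data are needed. The SAP records that it was written before data collection ended and the database was locked; if lock has not yet happened, the change can still be prespecified.
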